1.1. DESCRIPTION OF INVESTIGATIONAL PRODUCT

KPI-121 0.25% ophthalmic suspension contains submicron particles of LE suspended in a formulation consisting of excipients that have been used in other FDA-approved ophthalmic products. Kala is developing this improved LE formulation for the treatment of ocular inflammatory disease including inflammatory MGD.

KPI-121 0.25% ophthalmic suspension contains 0.25% (w/v) LE in an essentially isotonic formulation that is buffered to maintain pH 5.0 – 7.0. It is a sterile, aqueous submicron suspension of LE and is filled in a white, low-density polyethylene plastic dropper bottle with a white, controlled-drop polyethylene tip and a polypropylene cap. Each bottle contains 5.5 mL nominal fill volume.

The vehicle control has the same composition as KPI-121 0.25% ophthalmic suspension except it does not contain LE. The vehicle is essentially isotonic and is buffered to maintain pH 5.0 – 7.0. It is a sterile, aqueous solution supplied in the same white, low-density polyethylene plastic dropper bottle with the same white, controlled-drop polyethylene tip and white polypropylene closure as KPI-121 0.25% ophthalmic suspension.

1.2. JUSTIFICATION FOR ROUTE OF ADMINISTRATION AND DOSE SELECTION

KPI-121 will be administered as a topical ophthalmic suspension. Subjects will self-administer 1 to 2 drops of either KPI-121 0.25% ophthalmic suspension or vehicle QID.

Direct instillation is the most efficient method for delivery to the ocular surface and is an accepted and widely used method for topical application to the eye. This study will examine safety and efficacy of KPI-121 0.25% ophthalmic suspension versus vehicle dosed QID for 28 days in subjects with signs and symptoms of inflammatory MGD.

For additional details on the toxicology studies and the respective safety multiples, see the Investigator's Brochure.

1.3. GCP COMPLIANCE

This clinical trial will be conducted in compliance with the protocol, International Conference on Harmonization (ICH) guidelines, Good Clinical Practices (GCP) guidelines and other applicable regulatory requirements.

1.4. POPULATION TO BE STUDIED

Up to 750 subjects with mild to moderate inflammatory MGD will be screened for this study. Approximately 200 subjects will be randomized to either KPI-121 0.25% ophthalmic suspension or vehicle.

2. TRIAL OBJECTIVES AND PURPOSE

2.1. OBJECTIVE

The primary objective of this study is to investigate the safety and efficacy of KPI-121 0.25% ophthalmic suspension compared to vehicle in subjects with signs and symptoms of inflammatory MGD.

3. TRIAL DESIGN

3.1. PRIMARY EFFICACY ENDPOINTS

Comparison of mean [REDACTED] Severity Assessment Score between the KPI-121 0.25% ophthalmic suspension group and the vehicle group:

- Visit 4 (based on the mean score for the 3 days prior to Visit 4)

Comparison of mean posterior lid margin hyperemia [REDACTED]

[REDACTED] at Visit 2 between the KPI-121 0.25% ophthalmic suspension group and the vehicle group:

- Visit 4

3.2. SECONDARY EFFICACY ENDPOINTS

Comparison of mean [REDACTED] Severity Assessment Score between the KPI-121 0.25% ophthalmic suspension group and the vehicle group:

- Visit 6 [REDACTED]

Comparison of mean posterior lid margin hyperemia [REDACTED]

[REDACTED] at Visit 2 between the KPI-121 0.25% ophthalmic suspension group and the vehicle group:

- Visit 6

3.3. EXPLORATORY EFFICACY ENDPOINTS

Comparison of mean investigator-rated assessment of conjunctival hyperemia between the KPI-121 0.25% ophthalmic suspension group and the vehicle group:

- Visit 4
- Visit 6

Comparison of mean investigator-rated character of the meibomian glands' contents between the KPI-121 0.25% ophthalmic suspension group and the vehicle group:

- Visit 4
- Visit 6

Comparison of mean investigator-rated expressibility of the evaluated meibomian glands between the KPI-121 0.25% ophthalmic suspension group and the vehicle group:

- Visit 4
- Visit 6

Comparison of mean corneal fluorescein staining between the KPI-121 0.25% ophthalmic suspension group and the vehicle group:

- Visit 4
- Visit 6

Comparison of mean TFBUT between the KPI-121 0.25% ophthalmic suspension group and the vehicle group:

- Visit 4
- Visit 6

Comparison of mean [REDACTED] Frequency Assessment Score between the KPI-121 0.25% ophthalmic suspension group and the vehicle group:

- Visit 4 [REDACTED]
- Visit 6 [REDACTED]

Comparison of mean change from baseline (Visit 2) in posterior lid margin hyperemia [REDACTED] for subjects with greater than or equal to a grade of 1 in at least one posterior lid margin (i.e., RUL, LUL, RLL, LLL) at Visit 2 between the KPI-121 0.25% ophthalmic suspension group and the vehicle group:

- Visit 4 as compared to Visit 2
- Visit 6 as compared to Visit 2

[REDACTED]
[REDACTED]
[REDACTED]

Comparison of mean change from baseline (Visit 2) investigator-rated assessment of conjunctival hyperemia between the KPI-121 0.25% ophthalmic suspension group and the vehicle group:

- Visit 4 as compared to Visit 2
- Visit 6 as compared to Visit 2

Comparison of mean change from baseline (Visit 2) investigator-rated assessment of the character of the meibomian glands' contents between the KPI-121 0.25% ophthalmic suspension group and the vehicle group:

- Visit 4 as compared to Visit 2
- Visit 6 as compared to Visit 2

Comparison of mean change from baseline (Visit 2) between investigator-rated assessment of the expressibility of the meibomian glands the KPI-121 0.25% ophthalmic suspension group and the vehicle group:

- Visit 4 as compared to Visit 2
- Visit 6 as compared to Visit 2

Comparison of mean change from baseline (Visit 2) corneal fluorescein staining between the KPI-121 0.25% ophthalmic suspension group and the vehicle group:

- Visit 4 as compared to Visit 2
- Visit 6 as compared to Visit 2

Comparison of mean change from baseline (Visit 2) TFBUT between the KPI-121 0.25% ophthalmic suspension group and the vehicle group:

- Visit 4 as compared to Visit 2
- Visit 6 as compared to Visit 2

Comparison of mean change from baseline (Visit 2) [REDACTED] Severity Assessment Score between the KPI-121 0.25% ophthalmic suspension group and the vehicle group:

- Visit 4 [REDACTED]
- Visit 6 [REDACTED]

Comparison of mean change from baseline (Visit 2) [REDACTED] Frequency Assessment Score between the KPI-121 0.25% ophthalmic suspension group and within the vehicle group:

- Visit 4 [REDACTED]
- Visit 6 [REDACTED]

Comparison of the mean [REDACTED] Severity Assessment Score between KPI-121 0.025% ophthalmic suspension group and the vehicle group

- Visit 4 [REDACTED]
- Visit 6 [REDACTED]

Comparison of the mean change from baseline (Visit 2) [REDACTED] Severity
Assessment Score between KPI-121 0.025% ophthalmic suspension group and the vehicle
group

- Visit 4 [REDACTED]
- Visit 6 [REDACTED]

TABLE 1: SUMMARY OF EFFICACY ENDPOINTS
 (All comparisons will be between the KPI-121 0.25% ophthalmic suspension and vehicle groups)

Evaluation	Comparison	Visit	1°	2°	Exploratory
Investigator-Rated Assessment of Bulbar Conjunctival Hyperemia	Mean change from BL	6 vs. 2			X
████████ Severity	Mean values	4	████████	X	
████████ Severity	Mean values	6	████████		X
████████ Severity	Mean change from BL	4	████████		X
████████ Severity	Mean change from BL	6	████████		X
████████ Severity	Mean values	4	████████		X
████████ Severity	Mean values	6	████████		X
████████ Severity	Mean change from BL	4	████████		X
████████ Severity	Mean change from BL	6	████████		X

Evaluation	Comparison	Visit	1°	2°	Exploratory
Frequency	Mean values	4			X
Frequency	Mean values	6			X
Frequency	Mean change from BL	4			X
Frequency	Mean change from BL	6			X
Corneal Fluorescein Staining	Mean values	4			X
Corneal Fluorescein Staining	Mean values	6			X
Corneal Fluorescein Staining	Mean change from BL	4 vs. 2			X
Corneal Fluorescein Staining	Mean change from BL	6 vs. 2			X
Investigator-Rated Assessment of the Character of the Meibomian Glands' Contents	Mean values	4			X
Investigator-Rated Assessment of the Character of the Meibomian Glands' Contents	Mean values	6			X

Evaluation	Comparison	Visit	1°	2°	Exploratory
Investigator-Rated Assessment of the Character of the Meibomian Glands' Contents	Mean change from BL	4 vs. 2			X
Investigator-Rated Assessment of the Character of the Meibomian Glands' Contents	Mean change from BL	6 vs. 2			X
Investigator-Rated Assessment of the Expressibility of the Meibomian Glands	Mean values	4			X
Investigator-Rated Assessment of the Expressibility of the Meibomian Glands	Mean values	6			X
Investigator-Rated Assessment of the Expressibility of the Meibomian Glands	Mean change from BL	4 vs. 2			X
Investigator-Rated Assessment of the Expressibility of the Meibomian Glands	Mean change from BL	6 vs. 2			X
TFBUT	Mean values	4			X
TFBUT	Mean values	6			X
TFBUT	Mean change from BL	4 vs. 2			X
TFBUT	Mean change from BL	6 vs. 2			X

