Eligibility Criteria:	
Inclusion Criteria:
 
At Visit 1 and Visit 2, individuals of either gender or any race will be eligible for study participation if they:
 
1. Provide written informed consent and Health Insurance Portability and Accountability Act (HIPAA) authorization prior to any study-related procedures.2. Are 18 years of age or older.3. Are willing and able to follow instructions and can be present for the required study visits for the duration of the study. In addition, they must demonstrate:
a. Single-masked investigational product use compliance of at least 80% during the final week of the run-in phase ANDb. [REDACTED] compliance of at least 80% in the final week of the run-in phase.4. Upon examination at Visit 1 ONLY, have ALL 5 of the following criteria in the same or both eyes:
a. [REDACTED]

e. An unanesthetized Schirmer score [REDACTED]
[REDACTED]

5. Are women of child bearing potential (WOCBP), who are not pregnant or lactating and not sexually active (i.e., abstinent) for 14 days prior to Visit 1 and are willing to remain so through 30 days following Visit 6 or the last administration of the investigational product or until completion of the subject's first menstrual cycle following the last administration of the investigational product, whichever period of time is longer. Alternatively, WOCBP who are not abstinent must have been using one of the following acceptable methods of birth control for the times specified:

- a. Intrauterine device (IUD) in place for at least 3 months prior to Visit 1 through Visit 6 or last administration of investigational product or until completion of the subject's first menstrual cycle following last administration of the investigational product, whichever period of time is longer.
- b. Barrier method (condom or diaphragm) with spermicide for at least 3 months prior to Visit 1 through Visit 6 or last administration of the investigational product or until completion of the subject's first menstrual cycle following last administration of the investigational product, whichever period of time is longer.
- c. Stable hormonal contraceptive for at least 3 months prior to Visit 1 through Visit 6 or last administration of the investigational product or until completion of the subject's first menstrual cycle following administration of the investigational product, whichever period of time is longer.

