3.5. DESCRIPTION OF TRIAL DESIGN

This is a Phase 2, multi-center, double-masked, randomized, vehicle-controlled, parallel-group study designed to evaluate the safety and efficacy of KPI-121 0.25% ophthalmic suspension in subjects with inflammatory MGD.

This study will include up to 6 clinic visits, including 2 weeks of single-masked vehicle run-in followed by up to 30 days of investigational product dosing (KPI-121 0.25% ophthalmic suspension or vehicle).

Up to 750 subjects at up to 12 centers located in the United States (US) will be screened at Visit 1 (Screening). Subject meeting eligibility criteria will enter a 14-day run-in period of QID dosing (1-2 drops per eye of single-masked vehicle). Approximately 200 subjects will be randomized to KPI-121 0.25% ophthalmic suspension or vehicle.

At Visit 2, subjects who continue to meet inclusion/exclusion criteria (with the exception of Inclusion Criteria #4 and #7) will be randomized in an approximate 1:1 ratio to either 1) KPI-121 0.25% ophthalmic suspension administered as 1-2 drops in each eye QID for up to 4 weeks or 2) vehicle administered as 1-2 drops in each eye QID for up to 4 weeks.

The study eye will be selected based on the qualification criteria entered into the Interactive Web Response System (IWRS) for stratification at randomization. These scores are based on findings at Visit 1 only. If both eyes qualify for the study, the study eye will be designated as OD. Randomization numbers will be assigned to subjects as they are entered into the IWRS, based on the following 2 stratification criteria:

- Subject's Visit 1 (Day -14) [REDACTED] score [REDACTED]
[REDACTED] AND
- Visit 1 (Day -14) investigator-rated posterior lid margin hyperemia score [REDACTED]

The IWRS will assign masked study kit numbers, and bottles of investigational product will be dispensed at designated visits. The Sponsor, Investigators, and study staff will be masked during the randomization process and throughout the remainder of the study.

Subjects will return to the clinic for complete study evaluations at Visits 4 and 6 (Day 15 \pm 1 day and Day 29 \pm 1 day, respectively). Subjects will also return at Visits 3 and 5 (Day 8 \pm 1 day and Day 22 \pm 1 day, respectively) [REDACTED], evaluate ocular discomfort, and assess concomitant medication use and AEs. Subjects will discontinue dosing and be released from the study at Visit 6 (Day 29 \pm 1 day).

[REDACTED]

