A summary of events is provided in [Appendix 1](#). Assessments in this study will include:

- In-clinic subject-rated assessment of ocular discomfort ([Appendix 2](#))
- [REDACTED] severity and frequency assessments ([Appendix 3](#))
- Investigator-rated assessment of posterior lid margin hyperemia ([Appendix 4](#))
- Investigator-rated assessment of the character of the content of meibomian glands ([Appendix 4](#))
- Investigator-rated assessment of expressibility of meibomian glands ([Appendix 4](#))
- Investigator-rated assessment of conjunctival hyperemia ([Appendix 5](#))
- Unanesthetized Schirmer Test ([Appendix 6](#))
- BCVA ([Appendix 7](#))
- Slit lamp biomicroscopy ([Appendix 8](#))
- Corneal fluorescein staining ([Appendix 9](#))
- IOP measurement ([Appendix 10](#))
- Dilated ophthalmoscopy ([Appendix 11](#))
- [REDACTED]
- [REDACTED]
- TFBUT ([Appendix 14](#))

A study schematic follows ([Figure 1](#)).

[figure not shown]

FIGURE 1: STUDY SCHEMATIC

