9.1.2. Analysis of Efficacy

The primary analysis population will be the Intent-to-Treat (ITT) population, defined as all subjects randomized, for all analyses [REDACTED]

[REDACTED] A subset of efficacy analyses will be examined for the Efficacy Evaluable (EE) population, the definition of which will be outlined in the Statistical Analysis Plan and finalized prior to unmasking of study data pursuant to clinical data review.

The primary analysis of all ophthalmic efficacy measures will be based on the single study eye for each subject.

[REDACTED] Severity
Assessment Score between the KPI-121 0.25% ophthalmic suspension group and the vehicle group at Visit 4 (based on the mean score for the 3 days prior to Visit 2 and Visit 4); and (2) comparison of mean posterior lid margin hyperemia [REDACTED]

[REDACTED] at Visit 2 between the KPI-121 0.25% ophthalmic suspension group and the vehicle group at Visit 4.

Secondary and exploratory efficacy endpoints will be evaluated as elaborated in [Section 3](#).

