APPENDIX 4: INVESTIGATOR-RATED ASSESSMENT OF SIGNS OF MGD

Eyelid Margin Hyperemia (lower eyelid):

0 = Normal	Normal age-appropriate redness and vasculation.
1 = Mild	Slightly dilated blood vessels; vessels colored pink, present in greater than 25% of the lower eyelid margin
2 = Moderate	More apparent dilation of blood vessels; vessels red, present in greater than 25% of the lower eyelid margin.
3 = Severe	Increased vascularity of the eyelid margin; numerous and obvious dilated blood vessels, deep red in color, present in greater than 25% of the lower eyelid margin.
4 = Very Severe	Clearly increased vascularity of the eyelid margin; numerous dilated blood vessels deep red color, present in greater than 75% of the lower eyelid margin.

Character of Meibomian Gland Content (10 glands in the middle part of lower lid)

[figure not shown]
0 = Normal	Clear liquid
1 = Mild	Hazy, turbid liquid
2 = Moderate	Turbid liquid with clumps
3 = Severe	Solid (paste)
4 = No glands expressible	

The most severe finding in any one meibomian gland should be recorded for this evaluation

Expressibility of Meibomian Gland (10 glands in the middle part of lower lid)

0 = Normal	9 – 10 glands expressible
1 = Mild	6 – 8 glands expressible
2 = Moderate	3 – 5 glands expressible
3 = Severe	1 – 2 glands expressible
4 = No glands expressible	

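### Does the four-lid Visit 2 entry rule for the exploratory hyperemia change endpoint need to be redefined on the single study eye?

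*Combined protocol and SAP*

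**What the plan says.** The endpoint is the mean change from Visit 2 in posterior lid margin hyperemia, at Visits 4 and 6 (protocol synopsis and Section 3.3). It is restricted by this condition: "greater than or equal to a grade of 1 in at least one posterior lid margin (i.e., RUL, LUL, RLL, LLL) at Visit 2". The four abbreviations cover the upper and lower lids of both eyes. The text between the name of the measure and the restriction is blacked out, as are three lines after the endpoint in Section 3.3.

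Other provisions that bear on it:

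- Section 9.1.2: "The primary analysis of all ophthalmic efficacy measures will be based on the single study eye for each subject". The same section then refers secondary and exploratory endpoints back to Section 3.
- Section 3.5, on the scores that select the study eye: "These scores are based on findings at Visit 1 only". Also: "If both eyes qualify for the study, the study eye will be designated as OD".
- Section 4.1, criterion 4: "Upon examination at Visit 1 ONLY, have ALL 5 of the following criteria in the same or both eyes". This criterion is not re-applied after the vehicle run-in, because Section 3.5 says "subjects who continue to meet inclusion/exclusion criteria (with the exception of Inclusion Criteria #4 and #7) will be randomized".
- Section 3.5 refers posterior lid margin hyperemia to Appendix 4, where the visible scale is headed "Eyelid Margin Hyperemia (lower eyelid") and grades 1 to 4 are described on the lower lid margin.
- Section 9.3 makes every p-value outside the co-primary tests descriptive.

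**The concern.** The restriction looks designed to keep subjects whose hyperemia can still improve. If so, it should be applied to the lid whose change is analysed, and the visible text does not do that.

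Two routes appear to let in subjects with nothing to improve. First, a subject may have grade 1 or more only in the fellow eye: the study eye is fixed from Visit 1, is the right eye by default, and may have settled during two weeks of vehicle. Second, a subject may qualify only on an upper lid, for which the visible Appendix 4 gives no grade descriptions.

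Such subjects would pull the mean change in both arms towards zero and shrink the treatment difference. In a Phase 2 trial the size of that difference is the main thing a descriptive endpoint offers, so an unclear analysis set would make it harder to read.

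**Working it through.** **Is there a mismatch?** It depends on the blacked-out definition of the analysed score.

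| If the analysed score is | Fellow-eye entry | Upper-lid entry, study eye |
|---|---|---|
| Study eye, lower lid only | mismatch | mismatch |
| Study eye, upper and lower lids combined | mismatch | consistent |
| Both eyes combined | no mismatch | consistent if upper lids are included |

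The visible text does not choose between these rows. The single-eye sentence in Section 9.1.2 points to the first two. The reference of exploratory endpoints to Section 3, where four lids across two eyes are listed, leaves the third open.

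**What could it cost?** The protocol gives no figure for this endpoint. Its only sizing figure, 71 per group for 90% power (Section 9.2), has its effect size and significance level blacked out and does not size this subset. The following is therefore illustrative.

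Inputs: q, the share of the subset with a study-eye score of 0 at Visit 2, assumed to be 5%, 10% or 20%; a true difference of 0.50 grade in the other eyes, assumed; no treatment difference in grade-0 eyes, assumed; about 200 randomized (Section 1.4).

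1. Difference with these subjects kept: (1 − q) × 0.50 = 0.475, 0.45, 0.40.
2. Subjects concerned: at most q × 200 = 10, 20, 40, since the subset cannot exceed those randomized.
3. Interval width after dropping them, relative to keeping them:
   - if the standard deviation is the same either way, 1/√(1 − q) = 1.026, 1.054, 1.118;
   - if grade-0 eyes do not vary and the mean change in other eyes is near 0, 1/(1 − q) = 1.053, 1.111, 1.25.
4. Gain in signal-to-noise from dropping them is the effect ratio 1/(1 − q) divided by the width ratio:
   - first case: 1/√(1 − q), a gain of 2.6%, 5.4%, 11.8%;
   - second case: 1, no gain.

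**Worked example.** Take q = 10%, 100 per arm, SD 1 in other eyes, mean change 0 on vehicle and 0.50 on active, and grade-0 eyes fixed at 0.

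- Kept: the variances are 0.9 × 1 + 0.9 × 0.1 × 0.50² = 0.9225 (active) and 0.90 (vehicle). SE = √((0.9225 + 0.90)/100) = 0.135, and the ratio of difference to SE is 0.45/0.135 = 3.33.
- Dropped: SE = √(2/90) = 0.149, and the ratio is 0.50/0.149 = 3.35.
- The effect rises by a factor of 1.111 and the SE by 1.104. A simulation of 20,000 trials gave 1.105. The net gain in signal-to-noise is about 0.5%.

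**The case for a change.** The best case for a change is that it costs almost nothing. Before unmasking, a sentence could tie the grade 1 condition to the analysed lid score and say how upper lids are graded. The four-lid subset could be kept as a sensitivity analysis. No new data are needed, and the estimate would describe a population that can respond.

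Part of this stands. The four-lid list, the single-eye sentence and the lower-lid heading do not obviously fit together, and a reader would like to know which eye and lids are analysed. But that detail may sit under the redactions. Section 3.3 is blacked out at the place where the score would be named, and the assessment lists and the appendices have blacked-out entries too. Sections 9.1.2 and 9.5 also refer to a Statistical Analysis Plan that could hold it.

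The argument for redefining the subset is weaker. No section states that its purpose is to hold lids that can improve. Both eyes are dosed, so asking whether a subject has hyperemia in any lid is a reasonable subject-level question. A grade-0 eye can still worsen, so the assumption that it carries no treatment difference is the extreme case. The 11.8% gain needs q = 20% and grade-0 eyes as variable as the rest, although they can move in only one direction.

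**Conclusion.** No change to the plan is called for. The visible wording leaves a gap in an exploratory endpoint, and an analyst with the unredacted definition can fill it sensibly.

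The rule uses data collected before randomized treatment, so it cannot favour one arm. The p-values are descriptive, and no decision in the trial is shown to turn on this endpoint. If the mismatch is real, its effect is dilution by the factor 1 − q. Redefining the subset would trade that for a smaller set (90 instead of 100 per arm at q = 10%), a wider interval and a further step away from all randomized subjects. The signal-to-noise gain at q = 10% lies between nothing and 5.4%.

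These sizes rest on assumed values of q and of the 0.50-grade difference; the documents give neither. The study eye met all five Visit 1 examination criteria, most of which are blacked out, so affected subjects may be few, but that cannot be verified. The number of study eyes at grade 0 at Visit 2, and a study-eye version of the analysis, can both be produced from data already collected if a reader asks. The conclusion does not extend to the co-primary or secondary hyperemia endpoints, whose own Visit 2 condition is hidden.
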